Assessments will be completed primarily at the IU Health Neuroscience Center by trained assessors, but can be broken down into multiple shorter visits or completed in part by phone, if desired. [During the COVID-19 health crisis, all study visits will be completed by phone or Zoom.] Participants completing all baseline assessments will be randomized. Randomization will be stratified by age (60-69; 70 and over) and MRI completion. To address frequent moves and service changes in the population, we will obtain contact information for 2 relatives/friends at enrollment.

[figure not shown]
[After the IU Research Restart beginning June 1 2020, study visits will be completed by a combination of in-person and telephone measures until full in-person measures are allowed to resume. Biospecimen collection, imaging, and Viromeaging substudy enrollment will be included; written consent will be required.]

Interventions. As noted, a professional UX design team led a user-centered design research effort to integrate the speed of processing and MIND food interventions. First, five users evaluated application screens and functions rendered on Sketch (https://www.sketchapp.com/). Second, these same users experienced

tablet-operated, interactive prototypes created through an application called Axure (http://www.axure.com/). Third, the design was evaluated by an outside expert team including human factors and software engineers and design researchers. Finally, the MindSpeed app was evaluated in a different group of five users for one week (ages 52-76yrs). The pilot study involved a combination of interview sessions, iterative design and usability evaluation of the prototype, food delivery and reporting, and game play (BrainHQ). Some older adults with low education have limited reading skills, low computer familiarity, and limited eyesight. Thus, a major objective of the design work was to make the application easy for the target group to use. This appears to have been achieved. First time users reported "this is self-explanatory" and "I will know how to use after first time, pretty simple." Findings from the pilot indicate that participants will shop through the app, accept home delivered foods, play speed training games, and track incentives.

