We refer to our *MIND* intervention as MIND foods rather than MIND diet to emphasize that participants randomized to this arm will shop for and receive MIND food through the app. Participants will select foods from within the app (options can be modified based on reported food allergies). Selected foods will be delivered to the participant's place of residence or available for pick-up at Eskenazi Health locations once per week. The food options within the app will be restricted to those created from the Phenol-Explorer database(96) and approved by [name]. Having ordered the week's food, participants will be prompted each day of the week to report the type and amount of purchased food consumed. An incentive of \$1 for each daily report will be added to the cumulative incentive total.

The Control interventions are designed to mimic the activities of the MIND and Speed interventions. The food control participants will experience all of the features of the MIND food participants with the exception that the foods available to order will be limited to whole foods very low in polyphenols (e.g., corn, rice, potatoes, iceberg lettuce, pears, etc). Speed control participants will experience the same app features as Speed participants but in place of speed training will play inert games such as tic-tac-toe. All participants will be eligible for up to \$17/wk of incentives.

All participants will be asked to sign an iPad user agreement when they receive the iPad at the Randomization Visit. Intervention calendars and other "reminder" tools will be utilized to increase engagement with weekly game play and food reporting.

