Intervention Maintenance. After the 12-week post-training assessment, incentives and food deliveries will cease but participants will have continued access to BrainHQ. Those in the MIND or MINDSpeed arm will be encouraged to maintain MIND food consumption with utilization of the MINDSpeed Cookbook which details the foods and recipes used in the trial. Maintenance was chosen over total cessation of the intervention because it holds potential to maximize treatment potency, provides information on the rates of self-managed adherence (speaks to reach and effectiveness of the interventions), and should enhance subject retention. This phase of the study will provide information on the degree to which the trainings were incorporated into subjects' lifestyle in a sustainable manner. We will use intent-to-treat principles when analyzing the 6 month follow-up data. The adherence information from this phase of the study will be used in exploratory analyses. Subjects in the Food Control arms will receive the MINDSpeed Cookbook at the end of study participation.

Strategies for Treatment and Measurement Fidelity. Treatment fidelity and monitoring as defined by the NIH Behavior Change Consortium Strategies(97) and checklist(98) is enhanced by app-delivery and daily food and objective game/video data. A help call button on the app allows the participant to text research staff or request a call back (8 to 5, M-F). Staff will have access to the participant's treatment assignments. The staff on call will conduct supervised practice with the BrainHQ programs, and MIND food and food control interventions with access to our UX designer, [name], clinical nutritionist, [name], and training expert, [name] and, if needed, [name]. The staff will complete a 3-step certification process prior to working with enrolled subjects including: written test (passing score of 80%), individual module check out, and proctored mock counseling sessions with older adults using structured performance rating forms to judge quality. After certification, ongoing quality assurance checks will include observed counseling sessions once per month for first 1 month and every 3 months thereafter. A similar program of training, certification, and ongoing quality will occur for the Assessor, who will be blinded to treatment.

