Safety. We have outlined our protocols for identifying and responding to events and injuries in the Protection of Human Subjects section of the proposal (see Adequacy of Protection Against Risk). We have described standard regulatory reporting procedures in the Data and Safety Monitoring Plan (DSMP) and the operation of our Data Safety and Monitoring Board (DSMB). Cognitive training is relatively safe but anxiety and burden can occur and will be monitored. MRI is a safe procedure for people who do not have metal implants or other contraindications. Study personnel will screen participants for these risk factors prior to enrollment. Before

entering the MRI environment, participants will be re-screened for MRI contraindications per IU standards. Physical confinement or noise in MRI can be uncomfortable. All efforts are made to assure participant's comfort. Blood draws will be conducted by trained and certified staff. Finally, a small number of participants may develop depression, dementia, or physical dysfunction during the study. Should this occur, we will direct the subject to appropriate clinical care (i.e., PCP or specialty clinic as needed). We will also direct subjects to appropriate clinical care based on blood pressure and pulse values obtained during Baseline, Post-Training, or Follow-Up appointments in clinic. This is not a study procedure, but rather a process for addressing potential safety issues within the hospital environment.

Measures. All assessments will be completed by a trained, certified, and blinded Assessor; all data will be entered into Research Electronic Data Capture (REDCap). We have decades of experience completing assessments with older adult participants.

Unless otherwise noted, measures are taken at baseline (BL), immediate post-training (PT), and 6 month follow-up (FU). BL, PT and FU assessments may be conducted at Eskenazi, IU Health Neuroscience Center, participant's homes, or via telephone with abbreviated outcome measures as necessary. [During the COVID-19 health crisis, all study visits will be completed by phone or Zoom, and biospecimen collection, imaging, and Viromeaging substudy enrollment will cease.]

"Off-line" training is tracked via subject-report at PT and FU of all non-study training, either cognitive or physical. Participants will indicate frequency and duration of leisure cognitive, physical, and formal educational activities.(99)

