Feasibility Outcome Measures. We will track the number of potential participants approached, screened, and enrolled to gauge recruitment success using \geq 50% of eligible participants enrolled as the criterion. We will also monitor the safety, acceptability, and adherence of the app-delivered interventions and outcome measurements. Safety will be assessed by comparing adverse event rates, both serious (i.e., hospitalizations, falls, episodes of angina) and non-serious (i.e., anxiety) across treatment groups. The acceptability of the experimental and control interventions will be measured using self-report surveys assessing satisfaction (i.e., 1 = very satisfied, 3 = neutral, 5 = very dissatisfied) with scores from 1-2 indicating acceptability. Adherence will be documented by dates, episodes, and time spent in completing speed training modules and food reports. Maintenance will be determined from training data and diet scores from PT to FU. Creation of RCT logistical structure will be measured as printed manuals for app delivery and support (experimental and control conditions) and Assessor certification and quality assurances.

Cognitive Outcome Measures. Consistent with the conceptual model, the primary outcome is a cognitive function composite. Our executive cognitive composite (ECC) consists of verbal fluency (phonemic and semantic fluency),(103) Symbol Search from the WAIS-IV, (104) Trail Making Test (Parts A & B, sec to complete),(105) and Stroop Interference (number completed in 45 seconds on color-word trial)(106) for each participant at each occasion of measurement. Raw scores for each test are standardized using the baseline mean and standard deviation. A composite is then formed as an average of z-scores. In addition, List Learning from the Repeatable Battery for the Assessment of Neuropsychological Status (RBANS) will also be administered to assess new learning and memory. Cognitive outcome measures may be modified to accommodate illiterate participants, including but not limited to, removal of Stroop and COWA and modification of MMSE.

MIND Diet Score. At each assessment (BL, PT, and FU), we will complete an interviewer-administered food frequency questionnaire (FFQ). At BL, study personnel will use the subject's FFQ report generated by Viocare to guide a discussion on incorporating selected study foods into their diet during the 12 week intervention.

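### As written, the blinded Assessor who gives the primary cognitive tests may also take the diet interview at PT and FU, so blinding to the food arm is not protected

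*Combined protocol and SAP*

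**What the plan says.** All places are in the combined protocol and SAP.

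- **Measures:** "All assessments will be completed by a trained, certified, and blinded Assessor". No exception is made for the diet interview.
- **Strategies for Treatment and Measurement Fidelity:** the training and quality programme also covers "the Assessor, who will be blinded to treatment". Intervention support staff, by contrast, can see assignments.
- **MIND Diet Score:** at BL, PT and FU, "we will complete an interviewer-administered food frequency questionnaire (FFQ". The interviewer's role is not named. The only other people mentioned appear at baseline: "At BL, study personnel will use the subject's FFQ report generated by Viocare to guide a discussion".
- **Interventions:** in the food control arms, "the foods available to order will be limited to whole foods very low in polyphenols", with potatoes, rice, corn, pears and iceberg lettuce among the examples. The Significance section describes the MIND pattern as favouring leafy greens, berries, nuts and olive oil.
- **Intervention Maintenance:** deliveries end after PT, but the MIND arms are urged to continue and have a cookbook. The food control arms get the cookbook only when they finish the study.
- **Recruitment and Randomization:** "Assessments will be completed primarily at the IU Health Neuroscience Center by trained assessors", in the plural.

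**The concern.** The plan relies on a blinded Assessor to keep the primary outcome free of examiner influence. A diet interview after 12 weeks of delivered food is a plausible way to lose that blinding, because the two food conditions differ in kind and the interview asks about exactly that difference. The baseline FFQ is harmless, since baseline assessment precedes randomisation. PT and FU are the visits that matter, and both are named in the primary hypotheses in Specific Aims.

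The ECC is given by an examiner. Its tests are timed or counted, but someone still starts and stops the clock and decides which fluency responses count. The plan also allows tests to be dropped or modified for participants who cannot read (Cognitive Outcome Measures) and a reduced battery for those who cannot tolerate the full one (Study Considerations). It does not say who makes those decisions. All of this is better done without knowledge of the arm. A systematic shift from such knowledge would not shrink with sample size, and neither the Bonferroni adjustment nor the longitudinal model would remove it.

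**Working it through.** The plan gives no figure on blinding, so there is nothing to reproduce. The check is a reading of the text plus one count.

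**1. Who takes the FFQ?** Measures assigns all assessments to the blinded Assessor. MIND Diet Score requires an interviewer at three visits and names none. The study personnel mentioned there discuss the FFQ report at baseline; they are not said to conduct the PT or FU interview. Taken together, the literal reading gives the interview to the Assessor. A reading in which someone else conducts it is possible, but it is not written down.

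**2. Can the answers point to an arm?** The food control list is low in polyphenols, while the MIND pattern emphasises foods rich in them. Feasibility Outcome Measures uses diet scores from PT to FU to judge maintenance, so the plan itself expects the instrument to track MIND eating. The Analytic Plan hypothesises adherence of at least 80%; the better the adherence, the more the answers separate the food arms. The clue is still probabilistic: the FFQ records intake, not assignment.

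**3. Is there a safeguard?** I found no statement that the ECC precedes the FFQ, no separate interviewer for PT or FU, no request that participants keep their assignment from the Assessor, and no record of Assessor guesses.

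**4. Which comparisons are exposed?** Power and Sample Size plans six adjusted comparisons, which matches the number of pairs among four arms: 4 × 3 / 2 = 6. Two arms receive MIND food and two receive control food, so 2 × 2 = 4 pairs cross the food factor:

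- MIND food + Speed versus food control + Speed
- MIND food + Speed versus Double Control
- MIND food + Speed control versus food control + Speed
- MIND food + Speed control versus Double Control

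The other 6 − 4 = 2 pairs have the same food condition on both sides, so a guess about food does not favour either side. The second pair in the list is the primary specific aim.

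**5. How large could the bias be?** Let *b* be the shift in ECC score when the Assessor believes a participant receives MIND food. Let *p*₁ and *p*₀ be the proportions believed to receive it in the MIND and control food arms. The bias in a food-crossing comparison is then *b* × (*p*₁ − *p*₀). The documents give none of these quantities, so no number follows. Recording guesses would estimate *p*₁ − *p*₀; *b* would remain unknown.

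**6. Does order alone solve it?** Giving the ECC first protects the PT score at that visit. If the same person assesses at FU, what was learned from the PT interview is already known before the FU ECC. Whether the same person returns is not stated.

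**The case against.** The strongest reply is that the sentence in Measures is too general to bear this weight. Elsewhere the plan gives scans to an imaging team, blood draws to certified staff, comorbidity to a data manager and training time to the vendor's records. Non-Assessor staff already handle FFQ material at baseline, so the PT and FU interviewer may well be someone else. This stands in part: the plan leaves the interviewer unspecified. For that reason the conclusion is that blinding is unprotected, not that it will be lost.

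The clue is also imperfect. Participants choose their own foods within each arm, habitual diets overlap, and deliveries stop after PT, so the clue is probably weaker at FU. The ECC components are largely seconds or counts, and assessors are trained, certified and checked. These points limit the risk without removing it, since a guess only slightly better than chance is enough to matter.

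A reader might infer more than the documents support:

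- **That the off-line questions reveal the training arm.** They do not by design: "training is tracked via subject-report at PT and FU of all non-study training, either cognitive or physical". Study games fall outside the question, and control participants play games too. Only a chance remark would disclose the arm.
- **That the satisfaction items do so.** The plan describes "self-report surveys assessing satisfaction" on a 1 to 5 scale for experimental and control conditions alike, and does not give them to the Assessor.
- **That a single Assessor sees everyone at every visit.** Recruitment and Randomization uses the plural, so carry-over from PT to FU is possible but not established.
- **That the bias is some percentage of the 0.5 SD target effect.** The documents give no unblinding rate and no scoring shift, so any percentage would only restate an assumption.

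**Conclusion.** The concern holds for the food factor only. On the plan's own wording, the blinded Assessor who gives the ECC also conducts the FFQ at PT and FU, and nothing written protects that person from learning about the participant's diet. The potential reach is four of the six pairwise comparisons, including the primary one. The size of any bias is unknown.

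This rests on two assumptions: that no other document separates the roles, and that reported intake differs enough between food arms to support a better-than-chance guess. Carry-over to FU further requires the same person at both visits. If practice already separates the roles, the gap is one of wording. It is a cheap improvement worth making, not a flaw that invalidates the design.

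**What to change.** Amend Measures and MIND Diet Score to state that:

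1. The ECC and RBANS List Learning come first at PT and FU.
2. The FFQ follows, taken by an existing trained assessor or study staff member who does not test that participant's cognition at PT or FU. The staff who support the food intervention should preferably not take it.
3. Participants are told before each visit not to mention foods or games to the cognitive Assessor.
4. The Assessor records a guess of the arm straight after the ECC at PT and FU, with a do-not-know option, and guesses are summarised by arm. A correct guess may also reflect visible improvement, so the summary is descriptive.

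The second item also closes the carry-over route, because the person testing at FU will not have heard the PT interview.

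The cost is visit order, some scheduling and some existing staff time; no new measure is needed beyond the recorded guess. The main drawback arises if intervention staff have to take the FFQ: they know the assignment and support the food intervention, so the diet score could pick up desirability bias. That should be a fallback, not the default. If the roles are already separate in practice, a clarifying sentence on who takes the FFQ covers the second item; the order, the instruction and the recorded guess would still need to be written in.

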While dietary components support the creation of new neurons, cognitive training promotes integration of neurons into neural networks.(19-21) Speed of processing training, in particular, results in very large performance gains(22-24) that are maintained for years.(25, 26) "Speed training" targets fluid mental processing speed and reduces the length of time needed to process more and more complex information.(27) In a secondary analysis of data from the largest cognitive training trial ever conducted, we showed speed training had a large effect among participants with fewer than 12 years of education; the effect size was 50% larger in those with fewer than 12 years of education compared to the subsample with 16 or more years.(28) The training advantage in the less educated carried out to 5 years.

At this time, there are no published randomized trials of speed of processing training combined with MIND foods. Nor are there published randomized trials of MIND foods or speed training properly designed and powered to assess effects in older adults with low education. Using a 2x2 factorial design, we propose to test in a randomized controlled trial the effects of speed training and MIND foods in older adults with low education. The ultimate goal of this line of research is to prevent or delay AD in this vulnerable group.

This study will enroll older adults receiving care in Eskenazi Health who have 12 years of education or less. Interested and eligible individuals who consent to the study will receive a study-provided tablet running our professionally designed MINDSpeed app. The app will provide each participant with 12wks of access, support, and incentives for all 4 study arms: 1) MIND food + Speed training, 2) MIND food + Speed training control, 3) MIND food control + Speed training, or 4) MIND food control + Speed training control. We refer to the combinatorial MIND food and Speed training intervention as MINDSpeed, while the combination of food control and speed training control we refer to as Double Control.

The primary specific aim of this pilot clinical trial is to determine MINDSpeed effects on an executive cognitive composite (ECC) score relative to Double Control. The primary hypotheses are that MINDSpeed is more effective than MIND food or Speed training alone and all are more effective than Double Control in improving the objective ECC measure at immediate post-training and 6-month follow-up.

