In order to test the mediating effect of blood biomarkers, brain structure, and brain function variables we need to establish the association between the mediating variable and primary outcome, after controlling for the intervention effect. Such an association is evaluated using a partial correlation. With our sample size, we have more than 80% power at the 0.05 alpha level to test a partial correlation of 0.3 between mediating variables and the primary memory composite outcome. Effect modifiers include adherence, percent body fat, age, baseline cognitive status, comorbidity, and *APOE* ε 4 carrier status. Evaluation of moderating effects is an exploratory aim and detection of such effects requires large sample sizes. Our study is therefore only able to explore treatment moderators. In addition, our sample size provides accuracy with no more than 8% margin of error at the 95% confidence level for feasibility outcomes.

Analytic Plan: *Preliminary Analyses.* Baseline characteristics of participants will be compared across treatment arms. We will also compare the baseline scores on outcome measures across treatment arms. For continuous variables, means and standard deviations will be reported. Frequency tables will be reported for categorical variables. Normality of continuous outcomes will be examined using a normal probability plot. For highly skewed measurements, appropriate transformations will be applied to achieve approximate normality. Repeated measurements over time will be graphed as spaghetti plots and examined for outliers. All data will be examined for completeness. The baseline characteristics will be compared across treatment arms and between participants who do and do not complete the study. If any significant differences exist, we will control for differences in the subsequent analyses. Analysis will be performed under the intention-to-treat paradigm.

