Mechanism Analyses. Mechanistic hypotheses are that, relative to control, intervention arm participants will have greater hippocampal volume, enhanced DMN and CEN connectivity at PT, better metabolic function, higher levels of neurotrophic growth factors, and lower levels of inflammation and oxidative stress. Hypotheses will be analyzed using cLDA. With regard to MRI, scan analysis described immediately above will be performed on targeted pre-specified ROIs and followed by spatially unbiased whole brain voxel-based analyses. Supplemental analyses will compare across scan modalities to address the relative incremental contribution of each modality (e.g. hippocampal volume) to capturing the overall neuroimaging outcome.

Moderator and Mediator Analyses. Analyses will be performed to determine the role of adherence, years of education, age, baseline cognitive scores, comorbidity, and *APOE* ε 4 carrier status (an indicator of elevated ADRD risk) in moderating intervention outcomes using cLDA. We hypothesize in particular that participants with greater adherence, more education, and lower comorbidity will experience larger ECC score gains. A three-way interaction between potential moderators, intervention arm, and time of measurement will be included in the model and a significant three-way interaction indicates the moderating effect. To evaluate hypothesized mediators of the speed training and MIND foods (e.g., inflammation, growth factors, oxidative stress, hippocampal volume), we will use the approach proposed by Krull and Mackinnon (2011) (147) that allows the testing of mediating effects in clustered data. Using the change in ECC outcome from baseline as the dependent variable, a series of three mixed effects models, as outlined by Krull and Mackinnon, will be fit and regression coefficients from these models will be used to estimate the direct and indirect treatment effects.

The cLDA provides valid inference when data are missing due to random dropouts. Sensitivity analyses will be performed to examine to what extent the results are affected when dropouts are not missing at random. Analyses based on complete cases, mean imputation, and worst case imputation will be performed. In addition, a pattern mixture model will be used to allow different intervention effects for subjects with different missing data patterns. Results based on these models will be compared to results from cLDA.

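### As written, the primary composite averages Trail Making in seconds with higher-is-better scores and no sign reversal, so faster Trail Making lowers the outcome; reversal is probably intended but is not stated

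*Combined protocol and SAP*

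**What the plan says.** Cognitive Outcome Measures lists the ECC components: phonemic and semantic verbal fluency, WAIS-IV Symbol Search, Trail Making and Stroop. Units are given for two of them: "Trail Making Test (Parts A & B, sec to complete" and "Stroop Interference (number completed in 45 seconds on color-word trial". Construction then takes two steps: "Raw scores for each test are standardized using the baseline mean and standard deviation. A composite is then formed as an average of z-scores". Nothing is said about direction. The same section allows Stroop and COWA to be removed for participants who cannot read.

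Two other places show which direction is meant. Specific Aims states the primary hypotheses in terms of "improving the objective ECC measure at immediate post-training and 6-month follow-up". Moderator and Mediator Analyses expects that certain participants "will experience larger ECC score gains".

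Only one other rule could alter the raw scores, under Preliminary Analyses in the Analytic Plan: "For highly skewed measurements, appropriate transformations will be applied to achieve approximate normality". It concerns distributional shape, not direction.

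**The concern.** A participant who completes Trail Making faster has a lower raw score and so a lower z-score. Averaged without a sign change, that improvement pulls the ECC down while improvements on the other tests push it up. The composite then mixes a level of performance with its opposite, and contradicts the direction in which the plan reads it.

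The ECC carries the primary hypotheses, the sample size, the primary constrained longitudinal model and the moderator and mediator analyses. Specific Aims describes speed training as reducing the time needed to process information, so the plan gives no reason to expect a timed test to stay still. Correct scoring depends on the analyst inferring a step that the definition omits.

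**Working it through.** **The plan's own figure.** Power and Sample Size gives up to 50 per arm, 80% power, an effect above 0.5 SD, six Bonferroni-adjusted two-sided comparisons and a baseline to follow-up correlation of 0.7. With alpha = 0.05/6 = 0.00833 and residual variance 1 - 0.7² = 0.51:

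n = 2 × (2.638 + 0.842)² × 0.51 / 0.5² = 49.4, so 50 per arm (power 80.6% with 50 evaluable).

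The figure reproduces and does not depend on the sign of Trail Making. Whether 50 allows for the stated 15% attrition is a separate matter.

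**Mean shift under the literal rule.** Let p be the number of z-scores where higher is better, n the number where higher is worse, and t the Trail Making benefit divided by the benefit on the other tests.

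Share of the aligned mean shift that remains = (p - n·t) / (p + n·t).

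The documents do not say how many z-scores are averaged. Two readings at t = 1:
- Six scores (p = 4, n = 2): 2/6 = 1/3.
- Five scores, fluency counted once (p = 3, n = 2): 1/5.

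At t = 0 the share is 1. If only Trail Making improves, by 0.5 SD on both parts, the ECC moves by -2 × 0.5/6 = -0.17 (six) or -2 × 0.5/5 = -0.20 (five), instead of the same amount upward.

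**Effect in SD units.** The trial is powered in SD units, and the composite's SD also shrinks when positively correlated abilities enter with opposite signs. With k = p + n scores and an assumed common inter-test correlation r (all tests scored in the same direction):
- aligned variance = [k(1 - r) + r·k²] / k²
- literal variance = [k(1 - r) + r·(p - n)²] / k²
- share of standardised effect = share of mean shift × aligned SD / literal SD

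| Scores | r | Aligned SD | Literal SD | Share at t = 1 |
|---|---|---|---|---|
| 6 | 0.3 | √(15/36) = 0.645 | √(5.4/36) = 0.387 | 0.333 × 0.645/0.387 = 56% |
| 6 | 0.7 | √(27/36) = 0.866 | √(4.6/36) = 0.357 | 0.333 × 0.866/0.357 = 81% |
| 5 | 0.3 | √(11/25) = 0.663 | √(3.8/25) = 0.390 | 0.2 × 0.663/0.390 = 34% |
| 5 | 0.7 | √(19/25) = 0.872 | √(2.2/25) = 0.297 | 0.2 × 0.872/0.297 = 59% |

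A true 0.5 SD effect on the aligned composite becomes 0.28-0.40 SD (six) or 0.17-0.29 SD (five). If 0.7 is also kept as the baseline to follow-up correlation of the literal composite, power at 50 evaluable per arm is 24-58% or 7-28%.

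**Sensitivity to equal benefit.** At t = 0.5 the mean-shift share is 3/5 (six) or 1/2 (five). With six scores and r = 0.3 the standardised share is 0.6 × 0.645/0.387 = 100%, so there is no loss in SD units. With five scores and r = 0.3 it is 0.5 × 0.663/0.390 = 85%. At r = 0.7 both exceed 100%. The loss in SD units therefore depends on Trail Making benefiting about as much as the other tests. The loss in mean shift occurs whenever Trail Making improves.

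**Removed components.** Suppose COWA is the phonemic fluency test and the remaining scores are averaged (both assumptions). Then p = 2 and n = 2 in either reading, and at t = 1 the mean shift is (2 - 2)/(2 + 2) = 0.

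**The case against.** The strongest reply is that this is a scoring detail left out, not a wrong choice. The hypotheses fix the direction of the ECC, only one orientation of Trail Making fits it, and a competent analyst would reverse it. No stated figure changes. The point about intent stands, and it limits severity. It does not rescue the definition: the rule is specific about units and the standardisation reference, and followed exactly it gives a result opposite to the plan's own reading.

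A second reply is that 1/3 and 1/5 overstate the loss. That also stands. They describe the raw mean shift. A reader might take them as the share of detectable effect that survives, but the plan is powered in SD units, where the shares are larger at the assumed correlations.

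Two further inferences are tempting and unsupported. One is that the ECC will be, or has been, scored unreversed; nothing in the documents shows this. The other is that the primary result would come out with the wrong sign. With all components present, that needs a Trail Making benefit more than p/n times that on the other tests: 2 times (six scores) or 1.5 times (five). The documents give no per-test effects to suggest it. The threshold is not absolute, because it falls to 2/2 = 1 for participants with Stroop and COWA removed, under the assumptions above.

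**Conclusion.** The concern holds for the written definition. As stated, the ECC rule makes a Trail Making improvement lower the primary outcome, under every reading of how many scores are averaged, while the plan treats a higher ECC as better. Reversal is probably intended.

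The size is conditional on literal scoring, on equal standardised benefit across tests, and on equal inter-test correlations of 0.3 to 0.7, none of which the documents supply. On those terms about 56-81% of the standardised effect remains with six scores and about 34-59% with five. If Trail Making gains clearly less than the other tests, the loss in SD units shrinks or disappears, but the composite still counts a Trail Making gain as a decline.

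This should be fixed because it concerns the primary outcome. It does not undermine the design, the sample size calculation or the analysis model.

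**What to change.** In Cognitive Outcome Measures, state that the Trail Making A and B z-scores are multiplied by -1 before averaging, so that a higher ECC means better performance. If times are transformed for skewness, align direction after the transformation: a log keeps the direction, whereas a reciprocal already reverses it and needs no further sign change. If scoring has already been done, record which rule was used and when it was decided.

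The cost is one sentence, with no new data and no change to the model. As a separate, minor clarification, state how many z-scores enter the average, in particular whether the two fluency tasks and the two Trail Making parts count as one score or two.
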